1.4 Overview of Onapristone

Onapristone is a type I antiprogestin which prevents the PgR from dimerizing and blocks ligand-induced protein kinase-mediated phosphorylation of the PgR.(15, 34) Nondimerized PR does not bind to DNA.(20) This aspect is key to the activity of onapristone, as dimerization is necessary for binding with PREs in PR-dependent genes and subsequently with coactivators to induce transcription. In addition, onapristone blocks coactivator binding to gPR and stabilizes corepressor binding. Without functional PgR dimers and PRE binding, no PgR-dependent gene transcription can occur. Studies have been conducted to examine the ability of PgR to recruit a chromatin-remodeling complex to the promoter when bound to different classes of antagonists and the influence of this interaction on PgR dynamics and function *in vivo*.(27) contrast to mifepristone, onapristone reverses the assembly of DNA-bound PgR complexes induced by progestins.(23)

1.4.1.2 MethylNitrosourea-Induced Mammary Tumors

In a study of rats bearing methylnitrosourea (NMU)-induced mammary tumors, tumor-bearing animals were treated with onapristone or megestrol acetate alone or in combination with

[figure not shown]

Figure 3:Onapristone blocks estradiol-stimulated growth

tamoxifen for four weeks. Monotherapy with either onapristone or tamoxifen caused partial remission of tumors in 30% of animals. When both antihormones were administered concomitantly, 80% partial and 20% complete remission were achieved, while oophorectomy induced 22% partial and 67% complete remission (see Table 1).(40)

Table 1: Remission rates of NMU-induced mammary tumors in rats treated with onapristone, tamoxifen or a combination of both antihormones

	Complete Remission (%)	Partial Remission (%)
Control	0	0
Ovariectomy	67	22
Onapristone (3 mg/kg ^a)	0	30
Tamoxifen (5 mg/kg ^a)	0	30
Onapristone + tamoxifena	20	80

^a Daily SC treatment over four weeks, NMU = methylnitrosourea

With respect to tumor growth, the combination of onapristone and tamoxifen was as effective as ovariectomy (Figure 3).(40)

Therefore, it is reasonable to hypothesize that the antitumor effect of tamoxifen may be enhanced by the combination with onapristone.(40, 41)

1.4.1.3 Non-clinical PK and Metabolism of Onapristone

The PK of onapristone has been characterized in male and female SD rats and female cynomolgus monkeys, the species used in the nonclinical safety evaluation of onapristone. Following oral dosing, onapristone showed a rapid absorption in both nonclinical species, and a moderate clearance. The systemic plasma exposure of onapristone increased in an approximately linear manner between 10 and 90 mg/kg/day in female monkeys, after 28 days of administration. In monkeys, the mean ratio of the prominent metabolite *N*-desmethyl-onapristone (M1)/onapristone AUC_{0-t} ranged from 0.31 to 0.74 in the 10 to 90 mg/kg/day dose range. Overall, there was no notable sex difference in onapristone or M1 plasma exposure in rats. Renal clearance was a minor pathway of elimination for onapristone in chimeric mice. Incubation of sandwich-cultured human hepatocytes with onapristone did not reveal any significant excretion in bile canaliculi, suggesting that biliary excretion is not expected to be an important pathway of elimination in human.

Onapristone was highly protein bound in human female plasma with an unbound fraction of 0.56 ± 0.03%. Jang [1997] previously reported that onapristone does not bind to α-1-acid glycoprotein.

Twelve metabolites of onapristone were identified in rat, monkey and/or human liver microsomes. In humans, nine metabolites were observed with *N*-demethylation, mono-oxidation, and dehydrogenation as prominent metabolic pathways. None of the metabolites were unique to humans, thus, rat and monkey were appropriate toxicology test species. The chemical structures of M1 and M2 (di-*N*-demethyl onapristone) were confirmed using a reference standard. M1 formation kinetics was shown to be similar in female and male HLM.

Recombinant CYP phenotyping experiments suggested that M1 formation is predominantly mediated by CYP3A4 and CYP3A5, with minor contribution from CYP2C9. CYP3A4 and CYP3A5 were also the major isoforms responsible for the demethylation of M1 to M2. Similarly, using CYP-

specific chemical inhibitors in HLM suggested that M1 and M2 formation was predominantly mediated by CYP3A, and to a lesser extent by CYP2C8 and CYP2C9.

Onapristone did not reversibly inhibit CYP1A2 and CYP2D6. However, onapristone inhibited CYP2C8, CYP2C9 and CYP3A4, with IC₅₀ values in the range of 4.3 to 30 µM. Onapristone was a time-dependent inhibitor of CYP3A4. In a pilot study, CYP1A2, CYP2B6, CYP2C and CYP3A induction was observed using hepatocytes from a human female donor.

In agreement with the high permeability and lack of efflux of onapristone in Caco-2 cells, onapristone was not a substrate of the efflux transporters MRP2, P-gp, breast cancer resistance protein (BCRP) or the bile-salt export pump (BSEP) in human hepatocytes. In addition, onapristone was not a substrate of the sinusoidal uptake transporter MRP3. Onapristone was not an inhibitor of MRP2 or BSEP. Similarly, M1 did not inhibit BSEP in human hepatocytes.

1.4.1.4 Safety, Pharmacology, and Toxicology of Onapristone

Safety pharmacology studies were conducted to identify the potential adverse effects of onapristone on several physiological systems. Central nervous system (CNS) was evaluated using Functional Observational Battery (FOB) and respiratory was evaluated using whole-body plethysmography assessment. CNS and respiratory safety pharmacology endpoints were integrated into a good laboratory practice (GLP) compliant four weeks repeat dose rat toxicology study. Cardiovascular safety pharmacology endpoints were evaluated in a GLP-compliant cynomolgus monkey study and HEK293 cells transfected with hERG.

Table 2 Summary of Safety Pharmacology Studies

Organ systems evaluated	Species / Strain	Method of admin.	Doses (mg/kg)	Gender and N per group	Noteworthy findings
VPT1140 GLP compliant CNS	Crl:CD(S D) rats	Oral	0 (vehicle), 10, 30 and 90 mg/kg/day (twice a day dosing at 0, 5, 15 and 45 mg/kg, 12 hours apart) for 4 weeks followed by a 2-week treatment free period.	Female 4 rats per group	No effect in the neurobehavioral parameters as measured in an FOB. A small increase in piloerection resulted in a statistically significant difference between the vehicle and mid (30 mg/kg/d) and high (90 mg/kg/day) dose. No effects observed in 10 mg/kg/day dose, except for a trend for increases in tremors. Increase in bizarre behavior was observed in some animals treated with 30 and 90 mg/kg; there was a trend for increases in tremors in all test doses; no statistically significant effect was reached in any of the doses evaluated.

Organ systems evaluated	Species / Strain	Method of admin.	Doses (mg/kg)	Gender and N per group	Noteworthy findings
Respiratory					Onapristone did not alter respiratory parameters measured in the whole-body plethysmography assessment at 10, 30, 90 mg/kg/day daily dosing.
VPT1326 GLP compliant Cardiovascular: Arterial blood pressure, Lead II Electrocardiography (ECG)	Monkey/ Cynomolgus	Oral	0, 10, 30 and 90 mg/kg (1 day)	Males 4/group	10 and 30 mg/kg: no effects 90 mg/kg: transient decrease in heart rate of 38 bpm at 4 hours after treatment only; QT and QTcV increase up to 37 (average 29 msec) and 30 msec (average 25 msec) respectively from 2 to 10 hours after treatment. No changes on arterial blood pressure, QRS complex, PgR and QA intervals.
VPT1318 GLP compliant Cardiac electro-physiology	in vitro test (hERG assay)	NA	Phase A: 30 μ M Phase B: 1,3 and 10 μ M	Groups of 3 cells/ concentration	Effect level of 10 μ M (4.5 μ g/mL) in the hERG test was observed; indicated the potential to prolong QT No effects were present at a concentration of 3 μ M (1.35 μ g/mL)

1.4.1.5 Genotoxicity Status of Onapristone and Metabolites

The Ames test and *in vitro* chromosome aberration assays were negative, indicating a lack of genotoxicity and mutagenicity. Earlier mouse micronucleus testing was also reported to be negative.

1.4.1.6 Clinical Experience

Onapristone (ONA) is a type I antiprogestin which prevents the PRA and PRB monomers from dimerizing, inhibits ligand-induced phosphorylation and prevents association of the PR with its coactivators, thus, preventing PR-mediated DNA transcription.(42) In contrast to other antiprogestins, ONA does not allow the PR complex to bind to DNA, minimally modulates PR-mediated genes, and inhibits ligand-induced PR phosphorylation.(33, 34) clinical anticancer activity of ONA has been previously documented in patients with hormone therapy-naïve(43) or tamoxifen-resistant(19) breast cancer (BC).

Onapristone in endocrine sensitive malignancies

More recently, an open-label, multicenter, randomized, parallel-group, phase I study (target n = 60; NCT02052128) included female patients >18 years with PR+ tumors. Fifty-two patients were randomized to five cohorts of extended release (ER) onapristone tablets 10, 20, 30, 40 or 50 mg BID, or immediate release 100 mg QD until progressive disease or intolerance. Primary endpoint was to identify the recommended phase II dose. Secondary endpoints included safety, clinical benefit and pharmacokinetics. Tumor diagnosis included: endometrial carcinoma 12; breast cancer 20; ovarian cancer 13; other 7. Median age was 64 (36–84). No dose-limiting toxicity was observed with reported liver function test elevation related only to liver metastases. The RP2D was 50 mg ER BID. Median therapy duration was eight weeks (range 2–44), and nine patients had clinical benefit lasting at least 24 weeks, including two patients with APRpos endometrial carcinoma.

[figure not shown]
In terms of safety, no dose-limiting toxicity (DLT) was observed. Only transient elevations in LFTs occurred, mostly in patients with liver metastases and abnormal LFTs at baseline. Fifty-one patients discontinued ONA treatment for disease progression, and one for an AE (bilirubin G3 elevation, eventually deemed progression of disease in the liver). Refer to section 8.2 for additional safety information.

Clinical benefit rate (partial response and stable disease lasting for at least 24 weeks) was observed in 17% of all patients including one partial response in a patient with ovarian cancer who had three prior therapies and three breast cancer patients with stable disease lasting for more than 24 weeks. These three breast cancer patients received seven, seven, and three therapies, respectively, prior to receiving onapristone and two of these patients had liver metastases.

The authors concluded that clinical benefit with excellent tolerance was seen in heavily pretreated patients with endometrial, ovarian and breast cancer.(16)

1.4.1.7 Pharmacokinetics of Onapristone

In the phase I trial(16), plasma concentrations of ONA, mono-demethylated ONA (M1) and other metabolites in plasma and urine were analyzed with a validated ultra-performance liquid chromatography with tandem mass spectrometry detection (UPLC-MS/MS) assay. Results showed that ONA AUC and Cmax were dose-proportional across dose levels, with high correlation coefficients (R2 values are 0.76 and 0.97, respectively, see Figures 5 and 6). Average Tmax was 3.01 hours (2.71–3.2) vs 1.84 hours for ER versus IR formulations, respectively, and concentrations of drug were sustained longer with a 60% (± 20) relative bioavailability for ER vs IR formulation. Steady state for the ER formulation was attained before day 8, and the mean ONA minimum concentrations at steady state were up to five times those obtained at day 1; day 8 through levels were similar to day 1 for IR. There was no evidence of ONA accumulation at day 57. The observed mean t1/2 for the ER formulation was approximately 18.01 hours (range, 13.9 to 37), consistent with steady state achievement before day 8. ONA plasma concentration versus time curves suggest biphasic elimination.

1.4.2 Unmet Medical Need

1. The current standard of care treatment for stage IV, HR+/HER2- recurrent/metastatic breast cancer (MBC) includes treatment with one of the cyclin dependent kinase (CDK) 4/6 inhibitors (palbociclib, ribociclib, abemaciclib) in combination with one of the anti-estrogens as first-line therapy.(3-5) For patients with disease progression after front-line endocrine therapy, the fulvestrant plus palbociclib combination demonstrated a remarkable improvement in progression-free survival (PFS) compared with fulvestrant plus placebo in the PALOMA3 trial (median 9.5 vs. 4.6 months; HR 0.46, 95% CI 0.36-0.59).(3, 44, 45)
2. Upon disease progression, PI3 kinase /mTOR inhibitors are used in combination with endocrine therapy as the second-line regimen for disease progression.(6) Recently, alpelisib, a PI3Kinase inhibitor, was approved in combination with fulvestrant for PI3Kinase-mutated tumors, based on the SOLAR-1 trial data. This trial also reported a small cohort of patients who achieved a 15% RR with prior exposure to CDK4/6 inhibitor therapy.(7) Hyperglycemia, and diarrhea were main side effects of alpelisib, and 25% of the study patients discontinued alpelisib due to adverse effects.(7) Despite the promising data, both everolimus and alpelisib have concerning side effects, and are somewhat toxic and difficult to tolerate due to pulmonary toxicity, and hyperglycemia (4). While there are no approved treatments for anti-PgR-based regimens beyond progression on CDK4/6 inhibitors, it is anticipated that treatment with antiprogestrone agents, such as onapristone, may overcome the drug resistance due to the ESR mutations that develop over the time.(12)
3. Regardless, most patients progress on these agents, and ultimately develop endocrine resistance. While the worsening of disease is inevitable, not all patients suffer from high tumor burden, and those with oligometastatic disease, and low tumor burden continue to do well.(13) However, for patients who progress on the prior therapy with CDK inhibitors, PI3K, and mTOR inhibitors, systemic chemotherapy is the only option regardless of the disease burden, thus, emphasizing the critical need for novel treatments. Exploring later lines of therapy, previous trials utilizing single-agent tamoxifen reported a 10% ORR.(46) Everolimus plus exemestane in the second-line setting led to an ORR of 9.5% in the combination arm, compared to exemestane alone (0.4%)(6) In patients who had three prior lines of therapy, single-agent abemaciclib provided 20% response rates, median PFS six months (Monarch 1).(47) Therefore, based on these trials' data, the proposed study with a combination of onapristone plus fulvestrant may be considered promising for further study if an ORR of 20% is identified in patients with prior treatment with CDK4/6 inhibitors-based regimens.

1.5 Overview of Progesterone Receptor Imaging

Tumoral expression of PgR can be visualized and quantified through the use of a radiolabeled progestin, ¹⁸F-fluorofuranylnorprogesterone (¹⁸F-FFNP), and positron emission tomography/computed tomography (PET/CT) imaging (48-53). A “first-in-human” study involving 20 patients with invasive breast cancer has been published using FFNP-PET/CT imaging.(54) There were no adverse events, changes in vital signs, laboratory values or electrocardiograms, or clinically detectable pharmacologic effects. Dosimetry evaluation determined that the effective dose equivalent of ¹⁸F-FFNP is comparable to other clinically utilized PET imaging agents. ¹⁸F-FFNP uptake was greater in PR+ cancers compared to PR- cancers. Thus, ¹⁸F-FFNP PET appears to be a feasible method of imaging PgR in breast cancer patients.(48-54)

2 HYPOTHESIS AND OBJECTIVES

Table 3 Objectives and Endpoints

Objective	Endpoint
Primary	
Estimate the objective response rate (ORR).	Best overall response of CR or PR, as per RECIST 1.1.
Secondary	
To evaluate progression-free survival rate (PFS).	Time from date of enrollment to the date of first documented disease progression or death due to any cause.
Estimate the disease control rate (DCR).	Best overall response of CR, PR or SD lasting for \geq 24 weeks, as per RECIST 1.1.
To describe time to response and duration of response.	Time to response: Time from enrollment to first documented response (CR or PR). Duration of response: Time between the first date of documented response to progression or death due to breast cancer.
To evaluate the safety and tolerability.	Type, frequency and severity of adverse events and laboratory abnormalities according to CTCAE version 5.0.

3 STUDY DESIGN

3.1 General Description

A phase II single-arm trial of onapristone in combination with fulvestrant for women and men with ER-positive, PgR-positive or negative and HER2-negative locally advanced or metastatic breast cancer after progression on aromatase and CDK4/6 inhibitors. The study will enroll up to 39 patients.

3.2 Estimated Time for Study Completion

3.2.1 Primary Completion

The study will reach primary completion in approximately 36 months from the time the study opens to accrual.

3.2.2 Study Completion

The study will reach study completion 48 months from the time the study opens to accrual.

4 SUBJECT SELECTION

4.1 Checklist. Use the below checklist to confirm a subject's eligibility. For each subject, this checklist must be completed and maintained in the subject's chart.

4.2 Eligibility Criteria

No waivers of protocol eligibility will be granted. When clinical factors relating to an eligibility item are unclear or questionable, the study PI or study chair ([name] [contact] or [name], [contact]) can only provide guidance or clarification on eligibility.

Enrolling investigator to initial next to each eligibility criteria.

Inclusion Criteria

Each subject must meet all the following inclusion criteria to be enrolled in the study:

- _____ 1. Voluntary written consent must be given before performance of any study-related procedure not part of standard medical care with the understanding that consent may be withdrawn by the subject at any time without prejudice to future medical care.
- _____ 2. Men and women with advanced ER+, (PgR positive or negative), and HER2 negative breast cancer. Advanced is defined as locally advanced or locoregionally recurrent or metastatic and not amenable to curative therapy.
- _____ 3. Below-mentioned prior lines of therapy are allowed in the adjuvant and or metastatic HR+/HER2- setting.
 - Patients must have had prior endocrine therapy either in the adjuvant or metastatic setting (SERM (tamoxifen, raloxifene, toremifene) or any of the aromatase inhibitors (anastrozole, letrozole, exemestane), or oral SERD on a clinical trial, either in the adjuvant or metastatic setting (but not prior exposure to fulvestrant)
 - Patients must have received prior therapy with oral CDK4/6 inhibitors in the metastatic setting.
 - Other standard therapies in the metastatic setting (such as mTOR inhibitors) are allowed

- Patients who previously received any one of the standard adjuvant chemotherapy regimens in a curative setting are eligible for this study.
- One line of prior chemotherapy in the metastatic setting is allowed (i.e. any single agent or doublet cytotoxic chemotherapy, not limited to xeloda).

_____ 4. Histologically and/or cytologically confirmed diagnosis of ER+, PgR+/- and HER2- breast cancer by local laboratory at diagnosis of metastatic disease. Hormone receptor positivity is defined as ER and PgR positivity in at least 1% cells by immunohistochemistry (IHC). HER2-negative breast cancer is defined as a negative *in situ* hybridization test or an IHC status of 0, 1+ or 2+. If IHC is 2+, a negative *in situ* hybridization (FISH, CISH, or SISH) test is required.

_____ 5. Measurable disease, i.e., at least one measurable lesion, as per RECIST 1.1 criteria. A palpable, and measurable breast mass is acceptable.

_____ 6. ECOG Performance status \leq 2. ECOG PS: _____ Date: _____

_____ 7. Adequate organ function:

- AST, ALT \leq 2.5 times institutional upper limit.

AST: _____ ULN: _____ Date: _____

ALT: _____ ULN: _____ Date: _____

- Total bilirubin \leq 1.5 \times ULN, except for subjects with Gilbert's syndrome who may be included if their total bilirubin is \leq 3.0 \times ULN and direct bilirubin \leq 1.5 \times ULN.

T. Bili: _____ ULN: _____ Date: _____

If subject has Gilbert's syndrome:

D. Bili: _____ ULN: _____ Date: _____

- ALP \leq 2.5 times institutional upper limit with exception that ALP of $< 5 \times$ ULN is acceptable in patients with elevated with ALP due to bone metastases (in the absence of liver metastases).

ALP: _____ ULN: _____ Date: _____

- Serum creatinine $< 1.5 \times$ ULN.

Creatinine: _____ ULN: _____ Date: _____

- Absolute neutrophil count (ANC) $\geq 1000/\mu\text{L}$.

ANC: _____ Date: _____

- Patients with lymphopenia are eligible at the discretion of the treating provider.
- Hemoglobin (Hb) \geq 8g/dL.

Hemoglobin: _____ Date: _____

- Platelet count \geq 100,000/ μ L.

Platelets: _____ Date: _____

_____ 8. Female subjects must meet one of the following:

- Postmenopausal for at least one year before enrollment,
OR
- Surgically sterile (i.e., undergone bilateral oophorectomy),
OR
- Premenopausal is defined as someone who has had menses at any time in the preceding 12 months. Premenopausal women who are eligible for this trial will require a GnRH analogue and treating physician may choose to monitor the ovarian function with laboratory tests (FSH/LH/Estradiol) to ensure a complete menopausal status with cessation of menses.

_____ 9. Women of childbearing potential must have a negative pregnancy test within seven days of registration. Subjects must have a negative pregnancy test seven to 10 days prior to starting study treatment.

Date of negative pregnancy test: _____

_____ 10. An FFPE tumor biopsy block or up to 20 superplus frost slides with unstained histological sections at 4 micrometer thickness are required at the time of study entry. Archived tumor tissue acceptable (metastatic disease from non-bone and non-brain sites preferred, but primary breast or lymph node tissue is permitted) if obtained in the 18 months prior to study registration, otherwise a fresh biopsy will be required if deemed safe by the treating physician (minimal risk to patient) (see section 10.5.1). Confirmation of adequate and available tissue sample is to be determined by the site's pathologist. Tumor samples do not need to be shipped for eligibility purposes. Tumor samples do not need to be shipped until subject is confirmed eligible and is registered for treatment.

_____ 11. Ability to take oral medications (without crushing). Please refer to section 6.1.2 for directions on taking the study drug (onaprisone).

_____ 12. To participate in the optional ^{18}F -FFNP PET/CT imaging, the subject must have ER positive, HER2 negative, AND PgR positive disease and at least one extra hepatic lesion measuring at least 10 mm in size.

Exclusion Criteria

Patients meeting any of the following exclusion criteria are not to be enrolled in the study:

- _____ 1. Prior treatment with an anti-progesterone agent.
- _____ 2. Prior treatment with fulvestrant in the metastatic setting.
- _____ 3. Prior treatment with CDK4/6 inhibitors in the neoadjuvant/adjuvant setting.
- _____ 4. History of malignancy other than breast cancer within three years prior to registration except for adequately treated non-melanoma skin cancer, cervical carcinoma *in situ*.
- _____ 5. History or presence of clinically active, and symptomatic CNS metastasis: If the patient fulfills the following criteria, they will be eligible for the trial:
 - Completed prior therapy (including radiation and/or surgery) for CNS metastases \geq 28 days prior to the start of study treatment and CNS tumor is clinically stable at the time of screening and patient is not receiving steroids and/or enzyme inducing anti-epileptic medications for brain metastases.
- _____ 6. Subjects with any of the following conditions:
 - Clinically significant illness or systemic disease as determined by the treating physicians.
 - Active hepatitis or uncontrolled infection or any other clinically significant cirrhosis or other disease that, in the opinion of the investigator would pose a risk to subject safety or interfere with the study evaluation, procedures or completion. Testing for infectious hepatitis is not required for the study. Treating provider may choose additional testing if indicated clinically.
- _____ 7. Patients who have had systemic chemotherapy, or targeted therapy, within two weeks prior to starting study treatment or those who have not recovered from acute effects of any prior therapy to baseline or Grade \leq 1. Grade 2 or higher exceptions include alopecia, up to grade 2 neuropathy or other grade 2 AEs or lab values not constituting a safety risk in the opinion of the treating physician. NCI CTCAE v5.0 will be used
- _____ 8. Co-administration with any prescriptions during the four weeks prior to first onapristone dosing and concerns for possible drug interactions should be discussed with the pharmacist. Please review Table 6 for additional details.
- _____ 9. Patients who are pregnant or breast feeding.
- _____ 10. History of acute coronary syndromes (including myocardial infarction, unstable angina, coronary artery bypass grafting, coronary angioplasty, or stenting) or symptomatic pericarditis within 6 months prior to registration.
- _____ 11. Symptomatic congestive heart failure (New York Heart Association III-IV).

_____ 12. Clinically significant cardiac arrhythmias (e.g. ventricular tachycardia), complete left bundle branch block, high-grade AV block (e.g. bifascicular block, Mobitz type II and third-degree AV block).

_____ 13. Any episode of atrial fibrillation in the prior 12 months.

_____ 14. QT interval >480 msec.

_____ 15. Long QT syndrome or family history of idiopathic sudden death or congenital long QT syndrome.

_____ 16. Concomitant use of medication(s) with a known risk to prolong the QT interval and/or known to cause Torsades de Pointe that cannot be discontinued (within 5 half-lives or 7 days prior to starting study drug) or replaced by safe alternative medication.

_____ 17. Systolic blood pressure (SBP) > 160 mmHg or <90 mmHg at screening.

"I have reviewed all inclusion and exclusion criteria and confirm the subject is eligible."

(CRC Signature)

(Date)

(Investigator/Enrolling Physician Signature)

(Date)

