1.3 Overview of Fulvestrant

Fulvestrant is the first-in-class unique ER downregulator with no known agonist effects.(37) Fulvestrant binds, blocks and, unlike tamoxifen or other SERMs, degrades the ER, completely inhibiting ER signaling. As a result, there is less chance of the ER being activated by alternative pathways that are believed to cause resistance (e.g., growth factor-mediated mechanisms). Fulvestrant is approved for the treatment of HR+ metastatic breast cancer in postmenopausal women with disease progression following antiestrogen therapy. Premenopausal women who receive ovarian suppression with GnRH analogues (leuprolide, goserelin) also can be treated with fulvestrant for metastatic HR+ metastatic breast cancer.(2) However, in postmenopausal women without symptomatic visceral disease after recurrence or progression on an AI, current clinical practice and treatment guidelines also include fulvestrant as a single agent.(2)

In postmenopausal patients who experienced progression after prior endocrine therapy (either AI or tamoxifen), fulvestrant 500 mg emerged as the optimal dose based on the results of the CONFIRM study, which showed that the higher dose (500 mg monthly) significantly prolonged PFS compared to the 250 mg dose (mPFS 6.5 vs. 5.5 months; HR= 0.80; p = 0.006).(38)

The most common clinically significant adverse reactions occurring in $\geq 5\%$ of patients receiving fulvestrant 500 mg were: injection site reactions, nausea, bone pain, arthralgia, headache, back pain, fatigue, pain in extremity, hot flashes, vomiting, anorexia, asthenia, musculoskeletal pain, cough, dyspnea, and constipation. Pooled safety analysis (SmPC) identified aspartate aminotransferase (AST), alanine aminotransferase (ALT) or alkaline phosphatase increases in approximately 15% of the treatment population with grade 3 increases seen in 1–2%. There was no difference in rates of AST, ALT, and AP elevations between groups treated with 250 mg and 500 mg doses.(39)

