7.5.1.4 Embryo-Fetal Toxicity

Fulvestrant can cause fetal harm when administered to pregnant women. Women who are not post-menopausal or surgically sterile must be treated with a GnRH agonist to be eligible to participate. Women must not donate eggs or become pregnant during participation or for 6 months

after stopping the drugs. Male breast cancer patients participating in the trial must not donate sperm or get their partners pregnant during treatment or within 6 months after their last dose. Subjects who have sexual intercourse which may result in pregnancy will be required to use contraception during study participation and for 6 months after their last dose.

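### Inclusion 8 ties the checklist GnRH requirement to menses in the preceding 12 months, which is narrower than section 7.5.1.4 and misclassifies women with functioning ovaries and longer amenorrhoea

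*Combined protocol and SAP*

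**What the plan says.** Section 4.2, Inclusion 8, requires each female subject to meet one of three branches.

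- **Branch 1:** "Postmenopausal for at least one year before enrollment". No hormone level, age or cause of amenorrhoea is attached, and no other section defines the term.
- **Branch 2:** surgical sterility, explained as bilateral oophorectomy.
- **Branch 3:** "Premenopausal is defined as someone who has had menses at any time in the preceding 12 months". Women in this branch need a GnRH analogue. The physician may check FSH, LH and estradiol "to ensure a complete menopausal status with cessation of menses".

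Three other places bear on the same question.

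- Section 7.5.1.4: "Women who are not post-menopausal or surgically sterile must be treated with a GnRH agonist to be eligible to participate". This rule does not mention menses.
- Section 1.3: "Premenopausal women who receive ovarian suppression with GnRH analogues (leuprolide, goserelin) also can be treated with fulvestrant". Women under suppression are still called premenopausal here.
- Section 7.5.1.5 and the FSH/LH/estradiol row of the Study Calendar provide for hormone testing, but both are worded for premenopausal women.

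Section 4.2 also rules out eligibility waivers. It limits the study PI and chair to guidance or clarification on unclear items.

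**The concern.** Branch 3 classifies a woman by whether she has bled recently, while the question that matters is whether her ovaries still function. The two come apart when amenorrhoea is induced by treatment or follows hysterectomy. The branch also works against itself: cessation of menses is its stated aim, yet a woman who has met that aim for 12 months no longer fits its definition.

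At stake is whether sites give the same answer for the same woman. One site could turn away a suitably suppressed patient. Another could give fulvestrant to a woman with ovarian function without the checklist prompting suppression.

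Such patients can be expected. Inclusion 3 states "Patients must have had prior endocrine therapy either in the adjuvant or metastatic setting". It also says "Patients who previously received any one of the standard adjuvant chemotherapy regimens in a curative setting are eligible for this study" and "One line of prior chemotherapy in the metastatic setting is allowed". Section 1.3 expects some women to be treated under GnRH suppression. Several sites will apply the checklist.

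**Working it through.** The plan gives no figure on this point, so the check is textual. The inputs are Inclusion 8, sections 1.3, 7.5.1.4 and 7.5.1.5, and the hormone row of the Study Calendar.

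**1. The test case.** Take a woman with functioning ovaries, no bilateral oophorectomy, and no menses for at least 12 months because of (a) a GnRH analogue, (b) chemotherapy, or (c) hysterectomy with ovaries retained.

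**2. Apply Inclusion 8.** Branch 2 fails, because she has had no oophorectomy. Branch 3 fails, because she has had no menses in the window. Everything then depends on branch 1, whose key word is undefined.

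| Reading of branch 1 | Result for (a), (b) and (c) |
|---|---|
| Ordinary clinical meaning: functioning ovaries means not postmenopausal | No branch met; not eligible, even if on a GnRH analogue; no waiver |
| Complement of branch 3: no menses for 12 months means postmenopausal | Eligible; no checklist duty to start or continue suppression |
| Evident intent of sections 1.3 and 7.5.1.4 | Eligible, with a GnRH analogue |

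Neither reading of branch 1 gives the third row.

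**3. Add section 7.5.1.4.** It makes a GnRH agonist a necessary condition for women who are neither post-menopausal nor surgically sterile. Since every inclusion criterion must be met, it cannot admit a woman who meets no branch of Inclusion 8. Under the second reading it may not be triggered, because it uses the same undefined word. It also omits the oophorectomy qualifier on surgical sterility, so a site could count hysterectomy.

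**4. Add the hormone testing.** Section 7.5.1.5 has the provider judge menopausal status from laboratory tests and clinical parameters. Both that section and the calendar row address premenopausal women. Under the branch 3 definition, the woman in step 1 is not one.

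**5. Confirm that the design figures are untouched.** Section 9.2 continues with at least 2 responses in 21 and declares activity with at least 6 in 39. The probability of declaring activity is the sum over x = 2 to 21 of P(Bin(21, p) = x) × P(Bin(18, p) ≥ 6 − x). This is 0.0499 at p = 0.07 and 0.805 at p = 0.20, in line with the stated 5% and 80%. Nothing in Inclusion 8 enters this calculation.

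**The case against.** The strongest reply is that the protocol should be read as a whole. Section 7.5.1.4 is binding, since section 12.8 requires conduct in compliance with the protocol. On the ordinary clinical meaning, a woman with functioning ovaries is not postmenopausal, so that section would seem to give the intended answer: eligible, with a GnRH agonist. The treating provider judges menopausal status, the PI or chair can clarify, and UWCCC verifies eligibility at registration (section 5.2). The Study Operations Manual cited there is not available here and may define the term.

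Much of this stands, and it limits the point. An unsuppressed woman enters only if a site takes 12 months without menses as menopause. The reply does not rescue the suppressed woman, however: section 7.5.1.4 adds a condition but opens no branch of Inclusion 8. Clarification helps only if the site sees the item as unclear, and the supplied text gives UWCCC no definition to verify against.

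It is also fair to say that little harm is demonstrated. The embryo-fetal concern does not arise after hysterectomy. For other women it is partly covered by the pregnancy test in Inclusion 9, by Exclusion 9 and by the contraception rule in section 7.5.1.4. Inclusion 3 does not list GnRH analogues among prior endocrine therapies, and the documents do not say how often chemotherapy leaves a woman amenorrhoeic with functioning ovaries.

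A reader might infer something stronger: that the protocol contradicts itself, that Inclusion 8 holds its only suppression rule, or that the response rate is compromised. The documents support none of these. The two sections conflict only if the shared word is read in two ways, section 7.5.1.4 is a second rule, and nothing supplied links this wording to response.

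**Conclusion.** The point holds as a mismatch between the checklist and section 7.5.1.4. Inclusion 8 states a definition that misclassifies a recognisable group, so this is more than a missing definition. For all three causes of amenorrhoea, the outcome is either exclusion despite suppression or entry with no checklist duty to suppress.

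The number of women affected is unknown and cannot be derived from the documents. No effect on response rate, power or error rates is claimed. The conclusion assumes that ovarian function can persist through amenorrhoea from these causes, and that no definition in the Operations Manual settles the matter. The wording should be corrected, but the point does not threaten the primary analysis.

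**What to change.** Reword Inclusion 8 to say that amenorrhoea arising during or after a GnRH analogue or chemotherapy, or after hysterectomy without bilateral oophorectomy, does not by itself establish postmenopausal status. Such women enter through the premenopausal branch and must receive or continue a GnRH analogue, as section 7.5.1.4 requires.

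The exception is a woman whose postmenopausal status the treating provider documents at screening, off suppression, using the FSH/LH/estradiol tests already in the calendar. The sample must precede the first fulvestrant dose, because section 7.5.1.5 warns that fulvestrant can falsely raise estradiol on immunoassay. Widen the label of that calendar row to cover this group.

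A woman already on a GnRH analogue can simply continue it and need not stop for testing. A woman who was naturally postmenopausal before these treatments is unaffected. No protocol-wide age threshold is needed, and the judgement stays with the provider. A bare cross-reference to section 7.5.1.4 would not be enough, because it would carry over the undefined term.

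The cost is two or three sentences, one relabelled row, and a few more hormone tests of a type already listed.
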